#### **EXPECTED RESULTS:**

In this study, it is expected that in the patients who underwent elective surgery, the markers of glycocalyx damage will increase their values in the postoperative laboratory tests compared to the values of the baseline (control) laboratory tests. It is equally expected that in patients undergoing urgent surgery, generally in clinical states of occlusion, perforation or sepsis, with activation of the inflammatory response, dehydration with decreased oncotic pressure and generation of tissue edema and third space, the markers of damage of glycocalyx are already elevated in the baseline analysis, with a maintenance or greater elevation of its values in the postoperative period. Likewise, a correlation would be expected between glycocalyx damage markers and other markers involved in the inflammatory response, such as leukocytes, C-reactive protein, procalcitonin, and lactate; as well as with associated patient comorbidities that lead to endothelial degeneration, such as high blood pressure, obesity, diabetes, atherosclerosis, etc. If the results of this study were as expected, glycocalyx damage markers (Heparan sulfate and Syndecan-1) could be used together with other inflammatory markers (CRP, procalcitonin, etc.) and be very useful in postoperative follow-up. of surgical patients, being able to anticipate possible postoperative complications. However, if elevations in glycocalyx markers were not observed in the perioperative period, it could be due to a lack of the number of Time-course determinations; that is to say, that an elevation of markers did occur, but we would not have detected it in the measurement times; or a larger

study population might also be needed. In either case, the study could be completed in subsequent research projects.

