### **Secondary Objectives:**

- To analyze a possible correlation of the glycocalix damage markers with other analytical parameters (PCR, procalcitonin, lactate, complete blood count, coagulation and basic biochemistry).
- To analyze the possible relationship of glycocalyx damage markers with different parameters depending on the patient (age, sex and associated comorbidities) and the surgical intervention (surgical time, approach, type of surgery...).
- To analyze other clinical parameters that may indicate a possible postoperative complication and their relationship with markers of endothelial glycocalyx damage will also be studied.

**METHODOLOGY DESIGN:** The present work is about a clinical, prospective, observational, and longitudinal study of single center groups (Hospital Lluís Alcanyís, Xàtiva). Always after the approval of the Research Ethics Committee of said Hospital.

**STUDY POPULATION:** The study population (value of n) has been calculated on a population of 100 patients who will undergo surgery approximately one year. With a confidence level of 95% and a margin of error of 5%, a sample size of 80 patients has been calculated. These 80 patients will be of legal age, men and women, undergoing elective or emergency colorectal surgery (right hemicolectomy, extended right hemicolectomy, left hemicolectomy, sigmoidectomy, anterior resection of the rectum or abdominoperineal amputation).

**CHOICE OF PATIENTS AND INFORMED CONSENT:** The selection of patients and the drafting of the informed consent documents will be carried out in a reasoned manner as established in article 32 of the Declaration of Helsinki and in article 58.2 of the Research Law. Biomedical. It should be considered taking into account the Declaration of Helsinki of the World Medical Association in its latest revision. And according to its latest version of the Helsinki Declaration of Fortaleza (Brazil) October

2013. Patients will be included in the study upon preoperative hospital admission, after verifying compliance with the inclusion criteria. To participate, it will be necessary to sign the informed consent.

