#### **METHOD:**

Blood samples will be drawn from an intravenous line, in BD Vacutainer® LH PST™ II tubes with lithium heparin at different times: 1st) basal time (preoperative), at hospital admission; 2nd) 2 hours after the end of the surgery, 3rd) 6 hours after the end of the surgery, 4th) 24 hours after the end of the surgery and 5th) 48 hours after the surgery. The blood samples will be centrifuged at 3000 rpm/12 min and the supernatants will be collected and stored at -80°C until the determination of the markers. Plasma levels of Syndecan-1 and Heparan Sulfate will be determined by ELISA (Enzyme-Linked Immunosorbent Assay), PCR (C-reactive protein), procalcitonin, lactate, blood count, renal function, basic coagulation and general biochemistry techniques. The blood samples will be drawn by the nursing team of the general surgery hospitalization ward, and will be transported to the laboratory by the auxiliary staff of said hospitalization ward. The laboratory staff will be in charge of centrifuging the samples and storing the supernatants in the pertinent conditions mentioned above. Later, when all the samples have been collected, the determination of the markers will be carried out, and the result will be displayed through the Orion clinic computer program or in paper format, which will be delivered to me personally. In addition, all the usual anesthetic, surgical and

postoperative care protocols of the Institution (General and Digestive Surgery Department. Lluís Alcanyís Hospital) will be maintained for these patients.

**STATISTICAL ANALYSIS PLAN (SAP):** Continuous data are expressed as mean  $\pm$  standard deviation. The normality of the data obtained was determined with the Kolmogorov-Smirnov and Shapiro-Wilk tests. Differences between baseline values and different moments after the "time course" of plasma levels of glycocalyx damage markers and other parameters will be analyzed by one-way analysis of variance (ANOVA). Data sets in which F is significant will be examined for multiple comparisons by Tukey's test. The Pearson correlation coefficient (r) will be calculated between the values of the EG damage markers and other parameters. The possible differences between the different population subgroups will be examined with the Student's t-test.  $P < 0.05$  will be considered statistically significant. All statistical calculations will be performed using the SPSS program.

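### Subgroup and correlation analyses ignore urgency, which the plan itself expects to raise the markers, so comparisons by any factor linked to urgency are open to confounding

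*Combined protocol and SAP*

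**What the plan says.** The Study Population paragraph describes one sample of 80 adults "undergoing elective or emergency colorectal surgery". It does not say how many of each are expected.

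The second secondary objective relates the markers to age, sex and comorbidities, and to "the surgical intervention (surgical time, approach, type of surgery" and so on. The Summary also names comparison of clinical and surgical subgroups as a purpose of the time course.

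The SAP paragraph gives these questions two methods. "The possible differences between the different population subgroups" are to be examined with Student's t-test, and Pearson's r is to be calculated between the markers and other parameters. Significance is set at P<0.05. The only other analysis is a one-way ANOVA over time with Tukey's test. The SAP has no covariate, no stratification and no separate elective and urgent analysis of the other factors.

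Expected Results treats urgency as a determinant of the outcome: "It is equally expected that in patients undergoing urgent surgery, generally in clinical states of occlusion, perforation or sepsis", it is anticipated that "the markers of damage of glycocalyx are already elevated in the baseline analysis", and that values will stay at that level or rise further after surgery.

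**The concern.** Suppose urgent patients have higher markers whatever operation they receive, and a factor is more common among them. A two-group comparison by that factor then picks up part of the urgency difference. The plan supplies the first condition as its own expectation. The second is plausible for approach and type of surgery, and less certain for age and for each comorbidity.

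The correlations have the same weakness. Expected Results describes urgent patients as having an activated inflammatory response, so urgency may raise both the glycocalyx markers and CRP, procalcitonin or lactate. A correlation in the pooled sample could then arise partly from mixing the two kinds of patient.

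At stake is how the second secondary objective, and the correlations in the first, are read. An association reported as significant for approach, procedure or a comorbidity could reflect urgency alone, and nothing planned would show this.

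**Working it through.** **The plan's own figure.** The sample size "has been calculated on a population of 100 patients who will undergo surgery approximately one year", with 95% confidence and a 5% margin of error. Using the precision formula for a proportion, with p = 0.5 (not stated, assumed here):

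- n0 = 1.96² × 0.25 / 0.05² = 384.16
- n = 384.16 / (1 + 383.16/100) = 79.51, rounded up to 80

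The 80 is reproduced. It comes from a survey-precision calculation and makes no allowance for subgroup comparisons or covariates.

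**Inputs for the illustration.** From the documents: n = 80, alpha = 0.05 (two-sided assumed), and the direction of the urgency effect. Assumed, because the documents do not give them: the urgent share, the frequency of each factor by urgency, and the urgency effect d in SD of the marker within urgency groups.

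**Formula.** If the factor has no effect of its own, the expected unadjusted difference is d × (urgent share at one level of the factor − urgent share at the other).

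**Main example.** Take 25% urgent, open approach in 70% of urgent and 25% of elective patients, and d = 1.

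- Open overall: 0.25 × 0.70 + 0.75 × 0.25 = 0.3625
- Urgent among open: 0.175 / 0.3625 = 48.3%
- Urgent among non-open: 0.075 / 0.6375 = 11.8%
- Spurious difference: 1 × (0.483 − 0.118) = 0.365 SD

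In simulated studies of 80 patients the unadjusted t-test rejects about 30% of the time. A linear model with the factor and urgency rejects about 5%. The correlation between approach and urgency is 0.41, so adjustment multiplies the standard error by 1/√(1 − 0.41²), about 1.09.

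**Range.** With 25–35% urgent, open approach in 50–70% of urgent patients (25% of elective) and d from 0.5 to 1.5, unadjusted rejection runs from about 7% to 63%. With 12% urgent and a milder imbalance it is about 6% to 8%.

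**Second design.** Here 80 patients are split 40/40 by a factor with no effect (20,000 runs per cell). Entries are unadjusted rejection rates.

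| Urgent share in the two groups | d = 0.5 | d = 1.0 | d = 1.5 |
|---|---|---|---|
| 30% and 30% | 4.5% | 3.0% | 1.7% |
| 40% and 20% | 6.5% | 10.1% | 14.7% |
| 50% and 10% | 13.1% | 36.3% | 63.2% |
| 60% and 10% | 18.2% | 53.2% | 84.5% |

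With urgency in the model, the rate is 4.8% to 5.3% in every cell. The top row shows that a balanced factor suffers no inflation.

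**Correlations.** If urgency (25% of patients) raises two otherwise unrelated variables by 1 SD each, the pooled r is 0.25 × 0.75 / (1 + 0.25 × 0.75) = 0.1875 / 1.1875 = 0.16, although r is 0 within each urgency group.

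**The case against.** Three stronger readings are tempting, and the documents support none of them.

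- *The factor effects will be confounded.* Confounding also needs the factor to be associated with urgency, and the documents give no distribution of any factor by urgency. The ASA limit of III may also keep out some of the sickest urgent patients, which could shrink both the urgent share and its effect.
- *The plan states that urgent patients have raised markers.* It expects this, under a heading for expected results, and gives no size. It is a hypothesis of the study.
- *The objective cannot be answered by the planned tests.* The objective asks about a possible relationship, in an observational study whose primary aim is to estimate marker levels. A t-test does answer a question about marginal association. The 30% above is a false-positive rate only if the target is an association independent of urgency.

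Nor is every factor necessarily sent to a t-test: Pearson's r is the natural route for age and surgical time. It is equally unadjusted.

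What remains is this. The plan applies P<0.05 to these comparisons and hopes the markers will help anticipate complications, so readers will want to know whether an association is separate from urgency. Testing elective against urgent patients as one more subgroup would estimate the urgency effect but would not remove it from the other comparisons. Eighty patients is a fair reason to keep the model small, but one factor plus urgency is small.

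**Conclusion.** The point holds as a risk of confounding in secondary analyses. Three facts come from the documents: elective and emergency cases are pooled, urgency is expected to raise the markers, and the planned tests ignore it. The size rests wholly on assumptions. In the main example it is a spurious 0.365 SD and about 30% rejection, against about 5% with adjustment. Under mild assumptions the excess over 5% is only a few percentage points, and under balance it is nil. The link with urgency is plausible for approach and type of surgery and uncertain for age and individual comorbidities. The primary estimation of marker levels is outside this point. This is a cheap improvement, not a flaw that invalidates the study.

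**What to change.** For each factor and marker, prespecify a linear model (a mixed model where several time points are used), preferably on the log marker, containing the factor and urgency (urgent or elective). An analysis stratified by urgency would also serve. Report adjusted differences with 95% confidence intervals and keep the unadjusted comparisons as descriptive. For continuous parameters use the same adjustment, for example a partial correlation given urgency. Age may be added as a covariate. State in the SAP how a case is classed as urgent, and tabulate each factor by urgency so that any imbalance is visible.

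Do not adjust for the baseline marker when the question is how the marker level relates to a patient factor such as comorbidity. The plan describes comorbidities as leading to endothelial degeneration, so the baseline value may lie on the pathway. For example, if a comorbidity raises baseline and postoperative values by 0.5 SD each and the within-patient correlation is 0.6, adding baseline reduces the expected estimate from 0.50 to 0.5 × (1 − 0.6) = 0.20. Use baseline only where the stated question is perioperative change.

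The cost is a few lines of SAP text, slightly more analysis, and a modestly larger standard error for factors correlated with urgency (about 9% in the main example). Urgency is inherent to each case, so no new patients, samples or procedures are needed.

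### The analysis relating the markers to patient and surgical factors makes no adjustment for emergency versus elective surgery, so a difference due to urgency can be reported as one due to another factor

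*Combined protocol and SAP*

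**What the plan says.** The design paragraph describes a "clinical, prospective, observational, and longitudinal study of single center groups". The study population paragraph admits patients "undergoing elective or emergency colorectal surgery" to one cohort of 80, without stating how many of each are expected.

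The second secondary objective relates the markers to "different parameters depending on the patient (age, sex and associated comorbidities) and the surgical intervention (surgical time, approach, type of surgery", with the list left open.

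The section on expected results names urgency as a determinant of the outcome: "It is equally expected that in patients undergoing urgent surgery, generally in clinical states of occlusion, perforation or sepsis", "the markers of damage of glycocalyx are already elevated in the baseline analysis". After surgery the values are expected to stay at that level or rise further. The same section expects the markers to correlate with inflammatory markers, "as well as with associated patient comorbidities that lead to endothelial degeneration, such as high blood pressure, obesity, diabetes, atherosclerosis".

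The SAP paragraph lists one-way ANOVA with Tukey's test for the time course, the Pearson coefficient between markers and other parameters, and, for groups of patients: "The possible differences between the different population subgroups will be examined with the Student's t-test". Significance is P < 0.05. The paragraph contains no regression, analysis of covariance, partial correlation, stratification or matching.

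**The concern.** None of the factors in the objective is randomised, and several could plausibly be distributed differently in emergency and elective patients. A two-group t-test or a simple r takes one factor at a time and cannot separate it from urgency. If a factor is unevenly spread by urgency, and urgency moves the marker as the protocol expects, the crude comparison carries part of the urgency difference.

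The study could then report that an approach, a type of resection or a comorbidity is linked to glycocalyx damage when the difference comes from operating on sicker, urgent patients. It could equally miss a real link where the imbalance runs the other way. Listing urgent versus elective as one more subgroup would display the urgency effect but would not remove it from the other comparisons. Correction for multiple testing would not remove it either, because the comparison itself is shifted.

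**Working it through.** **1. The plan's own figure.** The finite-population formula for a proportion is n = N z² p(1-p) / [e²(N-1) + z² p(1-p)]. From the study population paragraph, N = 100, e = 0.05 and z = 1.96 (95% confidence). p = 0.5 is assumed, since none is stated. Then n = 100 × 0.9604 / (0.2475 + 0.9604) = 96.04 / 1.2079 = 79.51, rounded up to 80. The stated 80 reproduces. It is a precision calculation for a proportion and has no bearing on confounding.

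**2. Inputs for the size of the problem.** From the documents: 80 patients, alpha 0.05 (two-sided assumed), urgent patients expected to be higher. Not in the documents, and therefore assumed over a range:
- share of urgent cases f: 20-40%
- urgency effect d: 0.5-1.0 SD
- prevalence of a binary factor in elective and urgent cases: four patterns, from balanced to strongly unbalanced.

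**3. Expected false difference.** For a factor with no effect, the crude difference between patients with and without it is d × [P(urgent | factor) - P(urgent | no factor)]. With f = 30%, d = 0.8 SD, and the factor in 30% of elective and 70% of urgent cases:
- P(factor) = 0.3 × 0.7 + 0.7 × 0.3 = 0.42
- P(urgent | factor) = 0.21 / 0.42 = 0.500
- P(urgent | no factor) = 0.09 / 0.58 = 0.155
- false difference = 0.8 × 0.345 = 0.28 SD.

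If the prevalences are exchanged (70% elective, 30% urgent), the sign reverses: 0.8 × (0.155 - 0.500) = -0.28 SD. On average that would cancel a true effect of 0.28 SD.

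**4. False-positive rate.** Simulation of one marker value per patient, n = 80, 4,000 runs per setting. The factor has no true effect. Student's t-test on the factor alone is compared with a linear model of factor plus urgency.

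| Factor in elective v urgent cases | t-test, f = 30%, d = 0.8 | t-test, all settings | With urgency, f = 30%, d = 0.8 |
|---|---|---|---|
| 30% v 30% | 5.4% | 4.7-5.4% | 5.2% |
| 30% v 50% | 10.1% | 5.8-12.4% | 5.4% |
| 30% v 70% | 20.2% | 8.2-34.4% | 4.8% |
| 20% v 80% | 41.8% | 14.7-65.4% | 5.2% |

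With urgency in the model the rate is 4.2-5.7% over all settings.

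**5. Price in precision.** In a separate assumed case (25% urgent, d = 1 SD, factor in 30% of elective and 80% of urgent cases), the standard error of the factor effect is 0.243 SD unadjusted and 0.255 SD with urgency added; 0.255 / 0.243 = 1.05. A seven-term model with modest assumed correlations gave about 0.28 SD. These are single-time models; the repeated-measures model proposed below was not simulated.

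**The case against.** The strongest reply is that the objective is exploratory and speaks only of a possible relationship, and that a crude association is a valid answer to a descriptive question. It misleads only if read as the factor's own effect, which the protocol does not explicitly claim. This stands in part: it limits the weight of the point. But the comparisons are a stated objective judged at P < 0.05, and the protocol describes the comorbidities as leading to endothelial degeneration, which invites the reading that crude tests cannot support.

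A reader might also infer more than the documents allow:
- That the SAP orders each factor to be tested alone. It assigns no test to any named factor and does not define the subgroups. What can be said is that it lists no method that takes two factors together.
- That the protocol expects a large urgency effect. It gives a direction, before and after surgery, and no size.
- That imbalance is established. No distribution of any factor by urgency is given, and with balance there is no inflation. Equally, nothing in the design prevents imbalance; the limit of ASA III narrows the case mix but does not exclude emergencies.

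It may also be said that 80 patients cannot support a large model with every factor in it. A single mutually adjusted model would have a further fault: surgical time may lie on the path from approach or type of surgery to the marker, so including it could remove part of the effect being studied. That argues for small models by factor, not for leaving urgency out.

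**Conclusion.** The point holds as a gap in method for one secondary objective. The listed analyses cannot separate any factor from urgency, which the protocol itself expects to raise the markers. A factor unevenly spread by urgency can then show a false link, or a true link can be masked.

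The size cannot be fixed from the documents. Under the assumed ranges, the consequence runs from none (balance) through modest (mild imbalance) to serious (strong imbalance), so the figures show what is possible and do not predict this study's error rate. They were computed for a binary factor; no separate case was run for continuous age or surgical time.

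A reader might infer that the study's main result is compromised. It is not: the primary objective is to estimate marker levels over the perioperative period, and this point does not touch it. The change should be made because the method as listed can mislead and the remedy is cheap.

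**What to change.** For the second secondary objective, prespecify for each marker a linear model of the four postoperative samples (2, 6, 24 and 48 hours). One suitable form is a mixed model with a patient random effect, time, urgency and urgency-by-time, together with age, sex and the factor under study. Fit it separately for each factor. Leave surgical time out of the models for approach and type of surgery, and study it in its own model. Report adjusted differences with 95% confidence intervals as the result. Keep the t-tests and simple correlations, labelled as unadjusted description.

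The cost is SAP wording and a standard SPSS procedure. Apart from elective or urgent status, which the protocol already distinguishes, it uses only variables that the objective requires. Intervals will be slightly wider. Factors that overlap strongly with urgency may not be separable with 80 patients, and the report should then say so. For age, sex and comorbidities the adjusted figure compares patients of the same urgency. If such a factor itself makes emergency presentation more likely, that route appears only in the unadjusted figure, which is a reason to keep both.
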